The TJDBPS01 trial is designed as a multicentre, randomized, controlled, superiority trial with two parallel groups in fourteen pancreatic centres among 11 provinces in China, providing a minimum of >50 PDs annually. **(Supplementary file 1)** All the participating fourteen centres with pancreatic surgery expertise have performed ≥ 104 TLPDs and OPDs, respectively.¹⁵ Screening and identification of eligible patients will take place within the participating centres' pancreatic multidisciplinary team (MDT). All patients about to undergo PD will go through a standard evaluation: Contrast-enhanced multi-thin-slice CT scans (1 mm) with or without endoluminal ultrasound (EUS), which will be discussed by the MDT. Magnetic resonance imaging with diffusion-weighted imaging is applied to rule out the suspected metastasis before surgery. Patients recommended for resection on the basis of a high likelihood of a malignant lesion will be contacted and provided with a detailed consensus. Consent (version date 2018-03-20, Ver 1.0) will be obtained by an investigator who should comply with applicable regulatory requirements and adhere to the ethical principles in the Declaration of Helsinki. It is not necessary for patients to have a histological diagnosis of malignancy before surgery provided that the MDT has confirmed that the lesion is concerning enough to require resection.¹⁶ Randomization will be performed in a 1:1 allocation. The patients will be randomized into two groups: (1) patients who will undergo TLPD and (2) patients who will undergo OPD. This study is structured after the SPIRIT 2013 guideline defining standard protocol items for clinical trials. **(Figure 1)**

Study population

All adult patients with an indication for PD, including but not limited to pancreatic cancer, bile duct cancer, duodenal cancer and benign diseases such as mass-forming pancreatitis, will be evaluated and informed of the possibility to take part in the TJDBPS01 trial. After the consent form is signed, participants will be randomized into the two previously mentioned groups.

Patients and public involvement

Neither patients nor the public are involved in the conception, design or conduct of the study.

Participants eligibility

Inclusion criteria

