Inclusion criteria include (1) age between 18 years and 75 years; (2) histologically proven periampullary cancer, including pancreatic cancer, bile duct cancer, and duodenal cancer; (3) cStage I pancreatic cancer; (3) an indication for elective PD surgery; (4) feasibility for both TLPD and OPD (the subject can also undergo surgery according to the MDT); (5) patients understand the nature of this trial and are willing to comply; (6) patients are able to provide written informed consent; and (7) patients are treated with curative intent in accordance with international guidelines.¹⁷

Exclusion criteria

Exclusion factors include (1) distant metastases including peritoneal carcinomatosis, liver metastases, distant lymph node metastases, and involvement of other organs; (2) patients may undergo left, central or total pancreatectomy or palliative surgery other than PD; (3) patients with

high operative risk, as defined by the American Society of Anesthesiologists (ASA), with a score \geq 4; (4) synchronous malignancy in other organs or second cancer requiring resection during the same procedure; (5) pregnancy; or (6) patients underwent or needed neo-adjuvant therapy including medication or radiotherapy.

Interventions

TLPD surgical procedures

The standard operative technique is described as follows (**Figure 2**). Any small variations according to the surgeon's preference, such as a different order for surgical steps, a variation in approach or pancreatic anastomosis technique, will be allowed but must be recorded authentically in the case record form.

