anastomosis. However, the mattress sutures do not completely penetrate the pancreatic parenchyma but only enter the tissue half-way. The fifth and sixth mattress sutures are supposed to interlock in the anterior wall of the jejunal hole. The fourth layer of the anastomosis has been made between the anterior wall of the pancreatic stump and the anterior wall of the jejunum. Four incompletely transpancreatic interrupting 4-0 prolene mattress sutures are placed to close the gaps in the superoinferior margin of the anastomosis and strengthen the sutures on its anterior wall, achieving a pancreas-enteric anastomosis. Approximately 10 cm distally, an end-to-side hepaticojjunostomy is performed with running (bile duct dilatation of >5 mm) or interrupted (bile duct dilatation of ≤ 5 mm) sutures (Novosyn, BRAUN). Approximately 40 cm distal to the biliary anastomosis, an antecolic side-to-side gastroenterostomy is performed with the staple technique, and 2 layers of running 3-0 sutures (Novosyn, BRAUN) are used to close the gastric stump. Two 27 Fr surgical drains are placed through Winslow and the upper region in the PJ stoma. After haemostatic control, the trocars are removed. The specimen is extracted through an upper-middle incision, which is subsequently closed in layers together with the closure of the trocars. A video clip for illustrative purpose of the basic laparoscopic surgical procedure is available as **Supplementary file 2** and **Supplementary file 3**.

OPD techniques

The open pancreaticoduodenectomy will be performed by the same group of surgeons. A right sided rectus muscle abdominal incision is preferred for better exposure. The key steps are similar to those taken in the TLPD group. Since outcomes of open pancreatectoduodenectomy worldwide are promising and convincing, the surgical technique in the OPD arm reflects their usual practice; also,

the anastomoses will be performed according to each centre's protocol. Procedure variations according to the surgeon's preferences are allowed but must be recorded on the case record form. Two surgical drains are placed as in the TLPD procedure.

Conversion from TLPD to OPD

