predictors of missing values will be identified. The primary outcome analysis will be conducted according to the Intention to treat analysis and will be adjusted for the predictors of missing values as the sensitivity analysis. In addition, multiple imputations will be used to impute missing data, and the imputed data will also be analysed as part of the sensitivity analyses.

Participant timeline

The trial time schedule of enrolment is estimated to be a 2-year period, followed by a 2-year follow-up visit after discharge from the hospital. Once the eligibility of the patients is confirmed, randomization will be applied. When to apply the interventions is not strictly defined: every collaborating centre can make its own preferred adjustment, but this will usually be within 48 hours after the randomization. The assessments and visits for patients are mandatory in the first month, at 3 months, 6 months, 12 months and 24 months, with either telephone or in-hospital follow-up.

(Figure 3)

Sample size

Considering the primary outcome variable is the LOS and according to the latest systemic review,²⁰ MIPD was associated with a shorter length of stay than OPD was (mean difference [MD] -2.95 days, 95% confidence interval [CI] -3.91 to -2.00 days). Accordingly, the sample size is determined based on the primary objective of comparing the LOS between two surgical methods. Based on a mean difference of 2.95 days in the two surgical groups, using the two-sided test with 80% power at a significance level of 5%, the minimal sample size needed to detect a significant difference is calculated to be 274 patients in the TLPD group and 274 in the OPD group ($\alpha=0.05$,

$\beta=0.2$, power=0.8). Considering washout or loss of follow-up, we enlarged the sample size by 20% to compensate for withdrawal/dropout. Then, the final sample size is 656. Thus, there are 328 patients in each group.

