The null hypothesis (H0) is that the mean LOS of TLPD group is the same in OPD group. In another word H0: Mean LOSTLPD = Mean LOSOPD. The alternative hypothesis (HA) is that the mean LOS of TLPD group is not the same in OPD group. HA: Mean LOSTLPD \neq Mean LOSOPD. Two sample t-test are used then if the test statistic turns out that $p>0.05$, then it fails to reject the null. The mean LOS of TLPD group is the same in OPD group. Otherwise, if $p<0.05$, the null hypothesis is rejected. The mean LOS of TLPD group is not the same in OPD group. Base on the previous study and the hypothesis, a -2.95 days of mean differences should be obtained.

Recruitment

Each centre will screen eligible patients through the outpatient department or through advertising by the qualified surgeons. The duration of the recruitment period is estimated to be a 24-month interval depending on each centre's recruiting rate. No financial incentives will be provided to trial investigators or patients for enrolment in the recruitment period.

Participating surgeons and centre criteria

To prevent surgeon bias, participating surgeons must satisfy the following criteria: (1) they must have experience in performing more than 104 TLPDs, (2) they must have experience in performing more than 104 OPDs, and (3) they must have completed the Tongji Hospital TLPD training programme.

All the participating centres represent the largest pancreatic surgery centres in their region, ensuring that 50 PDs are performed annually. If willing to join the trial, each surgeon will be mandated to offer two recently unedited surgery videos for evaluation. The video should be sent to the Board and saved appropriately. Only when the Board approves the surgical techniques can the surgeon and his or her centre participate as a collaborator.

Randomization and allocation

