We applied the stratified randomized block design for the fourteen centres with a block number of 4, and the design is conceived using SAS statistical software (V. 9.3; SAS Institute, USA). The randomization is centralized through a computer-generated system and performed in a parallel fashion. A data manager who is independent of the data analysis or patient enrolment generated the randomization schedule. Allocation will be announced and handled out by the study coordinators only after a baseline assessment and the patient consenting to participate in the study. The randomization schedule will not be available to study recruiters or physicians. Allocation will be conducted by the independent data manager. Specifically, when appropriate patients are enrolled, the researcher will inform the data manager, and then the random number and exact treatment group will be returned simultaneously.

Blinding

The patients and surgeons are unblinded while the data collectors, outcome assessors, and data analysts are blinded. The primary endpoint of this study is the LOS and is not influenceable by the data collectors, outcome assessors, and data analysts. Since they are blinded and also are not

involved in the pre-, peri- and post-operative management of the patients, thus they have no determination of the LOS. The surgeons only perform the surgery and didn't involve in the postoperative management. The patients have little influence concerning the LOS, since once the discharge criteria are reached, they will be discharge immediately. Most of the criteria are objective conditions like do not need any intravenous infusion, incision fully recovered without infection, major organ functioning well and nearly normal haematological parameters. These conditions won't influenced by the patients even they are unblinded.

Data collection

Patient demographics: year of birth, sex, body mass index, surgical risk (ASA score), comorbidities, previous surgical history, main complaint, preoperative biliary drainage, preoperative blood samples (haemoglobin level, white blood cell count, and granulocyte: lymphocyte (G:L) ratio), plasma level of total bilirubin, carbohydrate antigen (CA) 19-9, CA 125, carcinoembryonic antigen (CEA), alpha-fetoprotein (AFP), date of admission, and income.

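### A single stated block value of 4 per centre in an open-label trial makes up to about 32% of allocations deducible if it is the block length; undisclosed varying sizes are a cheap improvement for allocations not yet issued

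*Protocol*

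**What the plan says.** Under Randomization and allocation the protocol states: "We applied the stratified randomized block design for the fourteen centres with a block number of 4". It gives no other size and does not say that sizes vary. Under Design: "Randomization will be performed in a 1:1 allocation".

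The same section on randomization describes several protections. Allocation is central and computer-generated, an independent data manager holds the schedule, the arm is released only after consent and baseline assessment, and recruiters and physicians cannot see the schedule.

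The Blinding section leaves patients and surgeons unblinded. Under OPD techniques: "The open pancreaticoduodenectomy will be performed by the same group of surgeons". On timing, Participant timeline says "Once the eligibility of the patients is confirmed, randomization will be applied", and of the operation that "this will usually be within 48 hours after the randomization".

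The inclusion criteria contain one clear judgement: "feasibility for both TLPD and OPD (the subject can also undergo surgery according to the MDT". Screening is placed within each centre's multidisciplinary team (Design). On recruitment the protocol says: "Each centre will screen eligible patients through the outpatient department or through advertising by the qualified surgeons".

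**The concern.** The listed protections keep the list hidden. They do not stop someone who knows the block length from counting. With two patients per arm in each block of 4, the fourth allocation always follows from the first three. If the first two go to the same arm, the last two are both known.

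Counting does not need the list, because the operation itself reveals the arm and the same surgeons operate in both arms. The block value is printed in the protocol, so centre staff may well know it.

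What is at stake is concealment at entry. Eligibility is settled before randomization and includes a view on whether both operations are feasible. If the next arm can be deduced, that view could be influenced, and the arms could then differ at baseline.

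**Working it through.** The protocol gives no predictability figure, so there is none to reproduce.

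**Inputs.** 14 centres, used as strata (Randomization and allocation); 1:1 allocation (Design); 656 patients (Sample size); 24 months of recruitment (Recruitment). Assumptions: patients are spread evenly over centres, and the observer knows the block length or set of sizes and sees all earlier allocations at the centre in order.

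**Patients per centre.** 656/14 = 46.9, that is 12 centres of 47 and 2 of 46 (12 × 47 + 2 × 46 = 656).

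**Block length 4, exact.** There are six equally likely sequences. Two of them have their last two allocations certain; the other four have only the last.
- Certain per block: (2 × 2 + 4 × 1)/6 = 4/3, so (4/3)/4 = 33.3%.
- By position, the certain share is 0, 0, 1/3, 1. The best guess is right with probability 1/2, 2/3, 2/3, 1, which sums to 2.833 per block.
- Centre of 47 (11 blocks plus 3 patients): 11 × 4/3 + 1/3 = 15, and 15/47 = 31.9%. Best guess: 11 × 2.833 + 1.833 = 33, and 33/47 = 70.2%.
- Centre of 46: 11 × 4/3 = 14.67.
- Whole trial: 12 × 15 + 2 × 14.67 = 209.3, and 209.3/656 = 31.9%.
- Unequal centres change little. For any centre of 20 or more patients the share lies between 30.3% (at 22 patients: 5 × (4/3)/22) and 33.3%.

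**Four blocks per centre, exact.** 47/4 is about 12, so length 12.
- The certain share over complete blocks is 2/(12 + 2) = 14.3%.
- At 47 patients it is 5.86/47 = 12.5%, with the best guess right 63.5% of the time.
- Whole trial: 12 × 5.86 + 2 × 5.40 = about 81.

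**Randomly varying sizes, simulated.** Centres of 47; sizes equally likely; the observer knows the set of sizes but not their order and updates on all earlier allocations.

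| Scheme | Certain | Of 656 | Best guess right |
|---|---|---|---|
| Fixed 4 | 31.9% | about 209 | 70.2% |
| Fixed 12 | about 12% | about 81 | 63.5% |
| 2 and 4 | about 11% | about 71 | 71.7% |
| 4 and 6 | about 6% | about 37 | 68.8% |
| 4, 6 and 8 | about 2% | about 15 | 67.5% |

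**Is the previous arm visible in time?** 24 months is 730.5 days, and 730.5/46.9 = 15.6 days between randomizations at a centre. If arrivals are Poisson (an assumption), the chance of a gap longer than 2 days is exp(−2/15.6) = 88%. So the last operation has usually, but not always, taken place before the next randomization.

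**Balance with 4, 6 and 8.** The largest possible difference between arms within a centre rises from 2 to 4. At 47 patients, about 5% of centres end with a difference of 3 instead of 1. The 95th percentile of the whole-trial difference rises from about 6 to about 8 of 656.

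**The case against.** **Certainty is the measure that flatters the change.** Someone inclined to select can act on a good guess. From fixed 4 to sizes 4, 6 and 8, best-guess accuracy falls by only 2.7 points, about 18 fewer correct guesses in 656 (0.027 × 656). With sizes 2 and 4 it would even rise slightly. This stands. A reader might infer that varying block sizes remove the predictability, and the figures do not support that.

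**The 32% is a ceiling.** It requires complete tracking in order and knowledge that the candidate is next. Imaging, team discussion, consent and baseline assessment come before randomization, and another patient may be randomized in between. This also stands. A reader might infer that a third of patients were selected with the arm known, or that length of stay is biased. The protocol supports neither. It does not say whether operating surgeons sit on the multidisciplinary team, the only recruitment role it gives surgeons is advertising, and no effect on length of stay can be computed from it.

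**Fixed blocks of 4 with central allocation contradict nothing in the protocol.** True, which is why this is an improvement and not an error. It is still more than preference: the stated safeguards leave end-of-block deduction open, and the change is specific and modest.

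**It may be too late.** The protocol describes the schedule as already generated and does not say how many allocations have been issued. The gain shrinks accordingly: 209 − 15 = 194 fewer certain allocations if none has been issued, about 97 if half have, about 49 if three quarters have.

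**Conclusion.** The point holds as a low-severity improvement. If the stated value is the block length, up to 31.9% of allocations (about 209 of 656) could be deduced with certainty, and the safeguards described do not prevent it. This rests on three assumptions: length 4, knowledge of that length at the centre, and complete tracking of earlier open-label allocations. Equal centre sizes matter little.

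The drop to about 2% belongs to sizes 4, 6 and 8, not to varying sizes in general. The gain is in certain allocations; guessing better than chance remains.

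The wording matters because it also allows four blocks per centre. On that reading the ceiling is about 12%, and moving to 4, 6 and 8 would be a trade-off: certain allocations fall from about 12% to 2%, while best-guess accuracy rises from 63.5% to 67.5%.

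**What to change.** 1. Establish whether the 4 is the block length or the number of blocks per centre, and correct the wording.
2. If it is the length, have the independent data manager draw randomly varying sizes within centre, for example 4, 6 and 8, for allocations not yet issued. Start in each centre when its open block is complete.
3. State in the protocol given to sites only that sizes vary, and keep the sizes in a document that sites do not receive.
4. If four blocks per centre were meant, correct the wording and do not move to 4, 6 and 8 automatically; weigh fewer certain allocations against better guessing first.

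Cost: a new list for the unissued part of the schedule, one protocol sentence, probably a formal amendment with ethics submission and notification of authorities (Protocol amendments section), and the slightly looser balance shown above. Allocations already issued gain nothing.

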- Only high volume, expert centres are qualified to participate the study. They have to provide (i) laparoscopically trained surgeons with ≥ 104 TLPD procedures performed, (ii) ≥ 104 OPD procedures performed and (iii) completed the Tongji Hospital TLPD training programme.
- This is the first randomized trial providing with a 2-year survival data after pancreaticoduodenectomy.
- The main limitation is as this study is carried out by a large team of physicians that consists of surgeons, gastroenterologists, radiologists, pathologists and oncologists in several districts, the coordination of the team becomes a big challenge.
- This trial is designed to compare two surgery techniques with an open label so that the patients and surgeons are not blinded for their interventions, however the data collectors and the analysts are blinded.

Word count 4999

INTRODUCTION

Pancreaticoduodenectomy (PD) is one of the most complex abdominal operations to perform, involving removal of the head of the pancreas, the duodenum and the common bile duct, and it is usually performed for the treatment of pancreatic cancer and the relief pain in chronic pancreatitis.^{1,2}

Introduced by Gagner et al, who performed the first total laparoscopic pancreaticoduodenectomy (TLPD) procedures in 1994, the use of laparoscopy in pancreas surgery has continued to grow rapidly because of its potential technical advantages, such as the precision of movements achieved using laparoscopic instruments and a three-dimensional view provided by the unique vision system.³

To date, many studies have confirmed the advantages of laparoscopic techniques in gastric, renal and cervical surgeries.⁴⁻⁶ However, only a few low-quality studies have reported the application of total laparoscopy in pancreas surgery or in PD surgery. Notably, recently performed meta-analyses comparing LPD and open PD (OPD) have been unsatisfactory due to the small number of studies of good quality.⁷⁻¹⁰ Most studies concluded that TLPD was associated with a reduction in estimated blood loss (EBL), a lower transfusion rate and a shorter length of stay (LOS) compared with OPD surgery. In addition, TLPDs have a much longer operative time than OPDs. Finally, there were no significant differences between the two procedures in terms of major complications or mortality.

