Conversion is defined as any TLPD group in which a skin incision is used for reasons other than trocar placement or specimen removal. Subjects allocated to TLPD who undergo intraoperative conversion to open pancreateoduodenectomy will be analysed in the TLPD group according to intention-to-treat principles. Reasons for conversion should be carefully recorded in the surgical record.

Postoperative management

Postoperatively, antibiotics will be administrated as well as either parenteral or enteral nutrition. Somatostatin analogs are not routinely used for preventing postoperative pancreatic fistula. The abdominal drains are kept in place for observation and will be removed if they are not productive and/or the presence of a pancreatic fistula or bile leakage is excluded. Amylase determination of the drains is measured on the third postoperative day or when a fistula is suspected following the ISGPF criteria. Patients are willing to be discharged home when reached criteria as follow: (1) do not need any intravenous infusion, (2) can orally take solid or semisolid food, (3) do not need analgesics or fully comfort by orally analgesics, (4) incision fully recovered without infection, (5) could get off bed without assistance, (6) walking at least 250 meters in plain road, (7) major organ functioning well and nearly normal haematological parameters. The surgeons operating are not involved in the

postoperative management hence can't influence the discharge of the patients.

Follow-up

All patients will be followed-up for a period of 2 years.

Withdrawal

All the patients will be free to participate in this study and can decide to withdraw at any time. If a patient withdraws, his/her information will not be recorded in the study. However, the research team can still collect outcome data from the healthcare records.

Outcomes measures

Primary outcome measure

The primary outcome variable is the postoperative length of stay.

Secondary outcome measures

The secondary outcome variables include the estimated blood loss, operation time, complication rate, mortality, CCI, R0 resection rate, and overall survival.

Missing data

Bias due to missing data will be investigated by comparing the baseline characteristics of participants with and without missing values. Depending on the extent of missing levels, the

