Surgery information: operation date, surgical approach (open or total laparoscopic), type of digestive tract reconstruction, anastomosis approach (intracorporeal, extracorporeal), anastomosis performance (linear stapler, circular stapler, hand-sewn or combinations), placement of intra-abdominal drain, placement of nasogastric tube, total operative time, each anastomosis time (pancreaticojejunostomy, cholangiohepaticojejunostomy, pancreatogastrostomy), texture of pancreas, diameter of the main pancreatic duct, estimated blood loss (EBL), intraoperative blood transfusion, conversion to open surgery, intraoperative complications, intraoperative death, and

extent of lymphadenectomy.

Histopathological information: surgical margin status (R0 resection rates), number of retrieved lymph nodes, number of positive lymph nodes, tumour location, size of the tumour, depth of invasion (T classification), lymph node status (N classification), AJCC pathological stage (the eighth edition),²¹ and histological type.²²

Postoperative clinical findings: length of postoperative hospital stays, postoperative blood transfusion, patient mobilization (postoperative day (POD)), liquid diet (POD), soft solid diet (POD), drain removal (POD), length of intravenous analgesic use, cost for hospitalization, cost for surgery, drain production and amylase, haemoglobin levels, white cell count, tumour marker level after surgery, type of complication, reoperation, and Clavien-Dindo grade.²³

Follow-up: date of last follow-up visit, adjuvant chemotherapy, adjuvant radiotherapy, patient status at last follow-up visit (alive, dead, or lost to follow-up), and disease-free or not during follow-up.

All the data will be placed into the local database via a data registry server managed by the data collection group. In this trial, the follow-up and statistical staff will be masked to the intervention arms.

Data management

In this study, the EDC data collection system will be used for data collection. The roles of the staff involved in data collection include the clinical research coordinator (CRC), clinical research associate (CRA), and others.

All staff involved in the data collection process are to be qualified to access the research database. Data collection must be collected in accordance with standard specification processes.

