Any modifications of the protocol that may impact the conduct of the study, potentially benefit the patients or that may affect patient safety, including changes in study design, sample size, and study procedures, will require a formal amendment to the protocol. Additionally, this would need to be submitted to the Hospital Ethics Committee and health authorities must be notified in accordance with local regulations.

Confidentiality

All study-related information and participant information will be stored securely at the study site with locked cabinets in areas with limited access. All local databases will be secured with a password-protected access system.

Publications

Each participating investigator, with equal right, will be able to access the data of the registry, perform statistical analysis, discuss the results and freely write scientific manuscripts. The manuscript must be approved by all the authors before publication.

Ethics and dissemination

Approval from the the Institutional Review Board Approval of Tongji Hospital, Tongji Medical College, Huazhong University of Science and Technology (TJ-IRB20180512) is received in May 2018. All patients signed an informed consent document before entering the study. (**Supplementary file 4**) Consent is obtained by the consultant or designated team member and is preserved by the data collection group. This study has gained ethical approval at both the central and local levels for each participating centers, and central ethical approval has been confirmed by the the Institutional Review Board Approval of Tongji Hospital, Tongji Medical College, Huazhong University of Science and Technology. The recruitment will not start at other centres in the trial until local ethical approval has been obtained. Participating in both groups does not imply any additional risk for the subjects included, since the groups will not be deprived of the application of the most up-to-date recommendations. Any results from this trial (publications, conference presentations) will be published in peer-reviewed journals and conference proceedings.

DISCUSSION

The TJDBPS01 trial is a multicentre, randomized controlled trial. The trial hypothesis is that TLPD

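### Data collectors are declared blinded, yet the data they collect name the operation performed; for outcome assessors and analysts the blinding claim has no supporting procedure

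*Protocol*

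**What the plan says.** The blinding claim appears three times in the protocol.

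- Blinding: "The patients and surgeons are unblinded while the data collectors, outcome assessors, and data analysts are blinded".
- Article Summary (strengths and limitations): after conceding that the trial is open label, "however the data collectors and the analysts are blinded".
- Data collection: "In this trial, the follow-up and statistical staff will be masked to the intervention arms".

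Other sections bear on whether that can be so.

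- Data collection, surgery information: the listed items include "surgical approach (open or total laparoscopic)", intracorporeal or extracorporeal anastomosis, and conversion to open surgery. The postoperative items include type of complication and Clavien-Dindo grade. All data go into one database managed by the data collection group.
- Conversion from TLPD to OPD, where the protocol gives this definition: "Conversion is defined as any TLPD group in which a skin incision is used for reasons other than trocar placement or specimen removal".
- Data management: the data-collection roles "include the clinical research coordinator (CRC), clinical research associate (CRA), and others", and all such staff are to be qualified for access to the research database.
- Randomization and allocation: "Allocation will be announced and handled out by the study coordinators". A data manager independent of analysis and enrolment generates the schedule.
- Publications: each participating investigator "will be able to access the data of the registry, perform statistical analysis, discuss the results" and write manuscripts. No starting point is given.

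**The concern.** In an open-label surgical trial, masking of the people who record, grade and analyse outcomes is the main remaining safeguard against ascertainment bias. The protocol claims that safeguard without qualification, and the Blinding section then uses it as a premise in arguing that length of stay cannot be influenced.

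For length of stay, who records it matters little, because it is a count between two dates. Complication type, Clavien-Dindo grade and the comprehensive complication index involve judgement. They bear directly on the second half of the main hypothesis in Objectives, that TLPD is equivalent to OPD in safety. The argument in the Blinding section is made for length of stay only and does not reach these outcomes. Knowledge of the arm could distort them in either direction: it could create an apparent advantage or hide a real difference. The second possibility matters because the Introduction itself reports an excess of laparoscopic deaths in an earlier multicentre trial (5 against 1).

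**Working it through.** The protocol gives no figure for this point, so the check is a comparison of sections, group by group.

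**Data collectors.** The claim is that they are blinded. The collected items include the surgical approach, which states the operation performed. They also include conversion, which the protocol defines only for patients in the TLPD group, so a recorded conversion identifies the arm even though the operation ended open. The Interventions section further requires technique variations in each arm to be written on the case record form. The surgery fields and the complication fields share one database, and the protocol describes no separation of forms or permissions. Nobody can enter the surgery fields and remain unaware of the arm. The two sections contradict each other for at least those collectors, and the claim makes no exception for them.

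**Outcome assessors.** The claim is that they are blinded and take no part in patient management. Their role is not defined: the protocol does not say who grades complications or from which records. Nor does any section give them the surgery form or the allocation. Follow-up is by telephone or in hospital with patients who know their operation and, in hospital, with incisions that differ by arm; no concealment measure is described. The claim is unsupported but not contradicted.

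**Analysts.** The claim is that they are blinded. The database holds arm-revealing fields, but an extract for the statistical staff could omit them. The Publications section allows all participating investigators to analyse the data. The Contributors statement shows that study contributors performed the operations, and the Blinding section says surgeons are unblinded. An unqualified statement that analysts are blinded does not sit with that access right, although masking of the designated statistical staff remains possible.

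**Illustration of what differential recording could do.** All shifts here are assumptions; the protocol gives no complication rate. Take a true rate of 30% in both arms, let one arm be recorded at p, and use 328 patients per arm (Sample size section) with a two-sided 5% chi-square test.

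Pooled SE = √(2 × p̄(1 − p̄)/328), where p̄ is the mean of 0.30 and p. Unpooled SE = √([0.30 × 0.70 + p(1 − p)]/328). With d = 0.30 − p, the probability of rejection is Φ((d − 1.96 × pooled SE)/unpooled SE) + Φ((−d − 1.96 × pooled SE)/unpooled SE).

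For p = 0.25: pooled SE = √(2 × 0.275 × 0.725/328) = 0.0349, unpooled SE = 0.0348, and the main term is Φ((0.05 − 1.96 × 0.0349)/0.0348) = 0.30. The second term is negligible.

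| Recorded rate in one arm | Probability of a significant result |
|---|---|
| 30% (no shift) | 5% |
| 29% | 6% |
| 28% | 9% |
| 27% | 14% |
| 25% | 30% |

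The table shows sensitivity to differential recording. It does not show that any such shift will occur in this trial.

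**The case against.** The strongest reply is that only a narrow inconsistency exists. Several stronger readings are tempting, and the protocol does not support them.

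- **That outcome assessors know the arm.** A reader might infer this from the shared database. No section gives them the surgery fields or the allocation, so protection of complication grading is not shown to be absent; it is only not described.
- **That the analysts are unmasked.** A field in the database need not be in the analysis extract. Coded arms and withheld fields may be set in a statistical analysis plan that is not available here, and their absence from the protocol is not an error.
- **That the coordinators who announce allocation also collect the outcomes.** Study coordinators and the clinical research coordinator may be the same people, but the protocol does not say so.
- **That investigators may look at arm-level data during accrual.** The access sentence stands under Publications and concerns analysis and manuscripts. It states no timing, which is different from permitting early looks. The Confidentiality section also provides for restricted storage and password protection.
- **That blood loss loses a protection it was promised.** It is estimated in theatre, where the approach is visible. Masking later staff would protect it little, so it falls outside this point.

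It can also be said that the protocol never states who enters the surgery form, and that the list of data-collection roles is open-ended. That is true, but it does not rescue the claim: these items are listed under Data collection and go into the data collection group's database, while collectors are called blinded without exception. This part of the contradiction stands.

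**Conclusion.** The statement is wrong as written for data collectors: those who enter the surgery data know the arm. For outcome assessors and analysts it is unsupported, and the open-ended investigator access fits poorly with an unqualified claim that analysts are blinded. An analysis plan could describe a masked extract, but it could not make the statement true for data collectors.

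Severity is low to moderate. The primary outcome is little affected. The exposure is confined to complication grading and the comprehensive complication index, and its size cannot be derived from the protocol. The conclusion for collectors rests on one reading: that people who enter items listed under Data collection are data collectors in the sense of the Blinding section.

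**What to change.** 1. In the Blinding section and the Article Summary, state that staff who enter surgery data are not blinded, and limit the claim to the roles for which masking is arranged.
2. Use form-level permissions in the electronic data capture system so that existing staff who enter the surgery form do not grade complications, score the comprehensive complication index or conduct follow-up.
3. Give the statistical staff an extract with a coded arm and without the approach, anastomosis and conversion fields until the primary analysis is fixed.
4. In the Publications section, state that investigator access to arm-level data begins only after database lock and completion of the primary analysis.

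The cost is wording, system role settings, some reassignment of data-entry duties at sites, and later data access for investigators. No endpoint, sample size or patient care changes. The fix does not protect estimated blood loss, and the report should describe that outcome as assessed without blinding.
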